9. RESEARCH DESIGN AND METHODS

The overall strategy is to perform a feasibility study of rapid ART initiation among PWH-OOC who are randomized (1:1) to an unblinded behavioral intervention “60-Minutes-for Health”, compared to a 60 minute time-and-attention control session focused on diet and nutrition.

Individuals eligible for participation will be enrolled and followed for 48 weeks. They will be offered a same day (or within 1 week) appointment to enable the initiation of ART within 7 days of contact. Eligible individuals, after completing informed consent, will start ART for HIV with Bictegravir/Emtricitabine/tenofovir alafenamide (B/F/TAF) or appropriate alternative therapy if B/F/TAF is not thought to be an optimal regimen. Individuals will undergo computer-generated randomization (1:1) to onsite 60-Minutes-for Health intervention vs an onsite theory-based time-and-attention control session focused on diet and nutrition. After completion of the intervention participants will receive standard-of-care case management services between day 0 and week 4. A 60-day supply of B/F/TAF or alternative will be provided for participants of both study arms. The timeline of visits and study interventions is summarized in **Table 1**.

Table 1. Schedule of Evaluations

Study Assessment	Baseline (Day 0)	Wk 1	Wk 2	Wk 4	Wk 4-8	Wk 12	Wk 24	Wk 36	Wk 48
Assessments									
Eligibility checklist	X								
Informed Consent/HIPAA	X								
Randomization	X								
Release of information ⁴	X			X			X		X
Limited history ⁵	X								
Concomitant medications	X								
Baseline Risk Assessments	X								
Follow-up Risk Assessments				X			X		X
Linkage to Care Assessment	X			X		X ⁶	X	X ⁶	X
STI Treatment/Referral Tracking ⁷	X								
Targeted physical examination	X								
Historical ART assessment	X								
ART Adherence Monitoring		X	X	X			X		X
Adverse Event Monitoring	X	X	X	X			X		X
Ensure Provision of ART	X ⁸	X	X	X ⁸					
ART acceptability survey				X					
Behavioral Services									
60 Min Intervention vs. Control	X								
Case Management	X	X ⁶	X ⁶	X					
Telephone follow-up		X	X						

Focus Group (optional)					X				
Laboratories									
INSTI HIV Rapid Test ⁹	X								
HIV Ultra RNA PCR	X						X		X
CD4/CD8 Panel	X								
GC/CT NAT (x3 sites)	X								
Syphilis EIA	X								
w/reflex to titer and TP-PA	X								
Comprehensive Metabolic Panel	X								
CBC w/diff	X								
HepBsAg	X								
HIV Genosure archive resistance test (w/Integrase)	X ³								

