Pregnant individuals will be assisted in establishing care with HIV providers with experience in treating HIV in pregnancy and will assist with establishment in care with obstetrics providers with HIV expertise if not done prior to enrolment. The schedule of evaluations will remain the same for pregnant participants.

Data collection: data collection will be performed at each visit according to the schedule of evaluations and entered into the Research Electronic Data Capture (REDCap) data management system. Participants will be requested to provide release of information (ROI) to allow capture of HIV primary care visit data, primary care visit details (clinical notes) and HIV viral load for the duration of the study (48 weeks).

Primary outcomes are:

- the proportion of individuals with HIV VL ≤ 50 copies/ml at week 24; and
- the number of clinical care visits ≥ 90 days apart between study enrollment and week 24 (window +12 weeks).

Secondary outcomes are:

- the self-reported initiation of ART;
- the proportion of participants with HIV VL ≤ 50 at week 48;
- the proportion of participants with ≥ 2 clinical care visits > 90 days apart between enrollment and week 48;
- to compare discrete genotypic susceptibility score (derived from banked archive genotype at enrolment) between individuals with and without virologic suppression at week 24 and 48; and
- to assess the acceptability of rapid ART through quantitative surveys at week 4 and among four focus groups help between week 4-8.

Statistical considerations: Based on preliminary data from the 60-Minutes-for-Health pilot study, we expect a difference of 30% in the proportion of participants with suppressed viral load at week 24 between study groups. Assuming a loss to follow-up of 20% and a 70% rate of viral suppression in the intervention arm, we will need to enroll 124 individuals to detect a significant difference ($p < 0.05$) in suppression ($\geq 30\%$) between the two groups. The proportion of participants with the primary and secondary outcomes will be compared using Fisher's exact test between intervention groups. 95% confidence intervals for the overall proportion of PWH-OOC that are on ART with HIV VL ≤ 50 copies/ml and the overall proportion that are in care at week 24 will be compared to the analogous proportions among acute and early HIV (AEH) participants undergoing rapid ART initiation. Comparison with this historical cohort will be performed using Fisher's exact test.

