10. HUMAN SUBJECTS

We will enroll 124 participants in this study. Prospective participants will be identified through a number of means to ensure an equitable representation of PWH-OOC:

1. Potential subjects from UCSD Owen Clinic that fulfill the entry criteria will be contacted and offered an appointment for study recruitment
2. Subjects identified in the UCSD emergency department HIV screening program will be contacted and offered an appointment for study recruitment
3. San Diego Public Health Department (SDPHD) has implemented routine evaluations of their local HIV surveillance data in conjunction with other data to identify PWH who may be OOC³³. This Data to Care program results in the evaluation of ~ 250 new cases per year in San Diego (~20-21 PWH-OOC a month), many of whom are found to be viremic and out-of-care. Once located, SDPHD will offer immediate transportation vouchers (Lyft) to and from the AVRC to expedite study enrollment and rapid ART start.
4. If after 12 weeks enrollment falls below ~7/month we will initiate an additional social media campaign (Facebook and Instagram). We will use the existing UCSD AVRC platform to promote study participation and work within our existing partnerships with local gay bars to increase our social media reach.

Inclusion Criteria:

- 18 years of age or older;
- documented HIV infection status (or rapid HIV will be repeated);
- out-of-care defined as not seen in HIV provider clinic for ≥ 6 months AND not receiving ART for ≥ 1 month (by self-report);
- available for follow-up according to schedule of evaluations.

Exclusion Criteria:

- Co-morbid condition(s) that in the opinion of the investigator could limit the participant's ability to comply with the visit schedule or safely initiate rapid ART (e.g. psychiatric comorbidities or suspected central nervous system opportunistic infection);
- Prior ART regimens that in the opinion of the investigator precludes selection of a treatment option likely to result in virologic suppression (e.g. documented treatment failure on INSTI based regimen and multiple prior NRTI, NNRTI and PI regimens or documented resistance mutations likely to result in treatment failure)
- Participants that are unable to speak sufficient English or Spanish to consent to the study will be excluded

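### Optional efficiency gain: Fisher's exact test is valid here but leaves part of the 5% unused; Boschloo's exact test recovers some power at the same ceiling and the same N

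*Combined protocol and SAP*

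**What the plan says.** The statistical considerations in section 9 give one rule for the randomised comparisons: "The proportion of participants with the primary and secondary outcomes will be compared using" Fisher's exact test, between the two randomised groups. The sample-size text just before it reads "we will need to enroll 124 individuals to detect a significant difference ($p < 0.05" and rests on three inputs: "we expect a difference of 30% in the proportion of participants with suppressed viral load at week 24 between study groups", "a 70% rate of viral suppression in the intervention arm", and 20% loss to follow-up. Section 10 confirms the total: "We will enroll 124 participants in this study". Allocation is 1:1 and computer-generated, and no blocking is described. Neither power nor sidedness is stated.

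The first primary outcome (viral load at or below 50 copies/ml at week 24) is binary. The second is listed in section 9 as a number of visits, while Aim 2 in section 6 describes a proportion in care at week 24.

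**The concern.** Randomisation fixes the arm sizes but not the total number of successes. Fisher's test conditions on both, so only a coarse set of p-values is attainable and the real type I error falls below the nominal level. A trial of this size then gives up some power without gaining anything that the plan asks for. Boschloo's test uses Fisher's p-value as its statistic but calibrates the cut-off over the unconditional distribution. It rejects every table that Fisher rejects, plus some more, and its type I error still cannot exceed 5%.

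What is at stake is modest: some power, and the verdict on borderline tables. For example, 35/49 vs 25/49, a difference of about 20 points, gives p = 0.061 by Fisher and p = 0.041 by Boschloo.

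**Working it through.** **Inputs.** From section 9: intervention rate 70%, difference 30 points (so control 40%), threshold 0.05, loss 20%, allocation 1:1. From section 10: N = 124. Assumed because not stated: two-sided test, 80% power.

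**Step 1: reproduce N.** With mean rate 0.55, the uncorrected size per arm is

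n = [1.960 × √(2 × 0.55 × 0.45) + 0.842 × √(0.7 × 0.3 + 0.4 × 0.6)]² / 0.3² = 41.97, i.e. 42.

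The continuity-corrected size is

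n' = (n/4) × [1 + √(1 + 4/(n × 0.3))]² = 48.4, i.e. 49.

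Allowing for loss, 49/0.8 = 61.25, rounded up to 62 per arm, or 124 in total. This matches the plan. Without the correction, 42/0.8 = 52.5, rounded up to 53 per arm, or 106. At 90% power the total is 140 without and 158 with the correction. So 124 is consistent with the corrected formula at 80% power, and that formula approximates Fisher's test.

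**Step 2: evaluable arms.** 124 × 0.8 = 99.2, about 49-50 per arm. If 62 per arm are randomised and each participant is lost independently with probability 0.2 (an assumption), the arms end exactly equal with probability Σ P(X = k)², X ~ Bin(62, 0.8), which is about 9%. Slightly unequal arms are therefore the usual case.

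**Step 3: exact size and power.** All 2×2 tables were enumerated for each pair of arm sizes. Fisher rejects at two-sided p ≤ 0.05. Boschloo rejects at the largest Fisher-p cut-off whose type I error, maximised over the common rate, stays at or below 5% (cut-off 0.068 at 49/49). Power is the exact binomial probability of the rejection region. Gains are in percentage points and were computed before rounding.

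| Evaluable (intervention/control) | Max size, Fisher | Max size, Boschloo | Power at 70% vs 40%, Fisher → Boschloo | Gain at 70% vs 50% | Gain at 87.5% vs 62.5% |
|---|---|---|---|---|---|
| 49/49 | 3.34% | 4.94% | 81.5% → 85.6% (+4.1) | +7.7 | +3.7 |
| 50/50 | 3.52% | 4.87% | 82.9% → 85.5% (+2.6) | +6.9 | +3.5 |
| 50/49 | 4.39% | 4.94% | 85.0% → 85.2% (+0.2) | +1.8 | +1.6 |
| 48/50 | 4.18% | 4.88% | 85.1% → 85.2% (+0.1) | +1.2 | +1.7 |
| 51/49 | 4.57% | 4.99% | 84.0% → 84.4% (+0.4) | +2.9 | +2.8 |
| 47/52 | 4.38% | 4.96% | 84.0% → 84.2% (+0.1) | +1.6 | +3.2 |

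The last column uses the pilot's 12-month retention rates (section 7, preliminary data) only as an illustration, because the plan assumes no week-24 in-care rate. At a more lopsided 54/45 that gain falls to 0.4 points.

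If losses were instead counted as failures and all 62 per arm analysed, Fisher's maximum size would be 3.84%. At the same three pairs of rates the gains would be 1.1, 5.7 and 3.0 points.

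**The case against.** The case for leaving the plan alone is strong, and most of it stands.

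- **No validity problem.** A reader might infer that the true error rate is about 3% where the plan promises 5%. The documents do not support that. Section 9 gives p < 0.05 as a threshold and does not claim that attained error equals 5%. Fisher's test respects the threshold as a ceiling, and the 3% figure needs exactly equal evaluable arms.
- **No shortfall in planned power.** A reader might infer that the trial is underpowered because of its test. But N = 124 fits the continuity-corrected formula, so the design already allows for Fisher's conservatism. At 49-50 per arm Fisher has 81.5-85.0% power at the design alternative.
- **Not shown for both primary outcomes.** The second is written as a count with no cut-off. The point reaches it only if it is analysed as the proportion in care of Aim 2, and changing the test does not supply the missing definition.
- **Small gain where it counts.** With unequal arms the gain at 70% vs 40% is a fraction of a point. Nor should four points be read as a general upper limit: the gain is 4.8 points at 48/48 for the same alternative and nearly 8 at 70% vs 50%.
- **Familiarity.** Fisher's test is well known and the study calls itself a feasibility study.

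What remains is that the gain is never negative and is larger when the true effect is smaller than assumed. That possibility is real: section 9 credits the 30-point difference to the pilot, but the pilot results reported in section 7 are retention at 12 and 24 months, not suppression at week 24.

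**Conclusion.** This is an optional improvement, not the correction of an error. Fisher's test at p < 0.05 is valid and matches the sample size. Its maximum two-sided size is about 3.3-3.5% with equal evaluable arms of 49-50 and about 4.2-4.6% in the unequal splits checked. Boschloo's test stays at or below 5% in every split checked and is never less powerful.

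For week-24 suppression the gain is slight at the design alternative unless the arms happen to be equal, and more useful if the true difference is nearer 20 points. For a binary in-care outcome at the illustrative rates it is about 1.6-3.7 points in the splits tabulated. These figures assume a two-sided test, a 40% control rate derived by subtraction, and analysis of the roughly 80% of participants who are followed up.

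**What to change.** In the statistical considerations of section 9, before any outcome is seen, replace Fisher's exact test by Boschloo's exact unconditional test for the randomised comparisons of proportions: week-24 suppression, the proportion in care as in Aim 2, and the binary secondary outcomes.

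Name the version: two-sided at 5%, with the two-sided Fisher p-value as the statistic, maximised over the full range of the common rate. This matters when arms are unequal. At 50/49 and 70% vs 50%, this version gains 1.8 points, while doubling the one-sided test gains 0.9. The software default should be checked against the text.

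Leave N = 124 unchanged. State whether Fisher's test is kept for the historical-cohort comparison, which is not randomised, so that having two exact tests in one paragraph is clearly deliberate.

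Cost: a line or two of text, a less familiar test name and slightly more computation. No extra participants are needed and error control is not weakened. The choice must be fixed in advance because borderline tables change verdict.

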10. HUMAN SUBJECTS

We will enroll 124 participants in this study. Prospective participants will be identified through a number of means to ensure an equitable representation of PWH-OOC:

1. Potential subjects from UCSD Owen Clinic that fulfill the entry criteria will be contacted and offered an appointment for study recruitment
2. Subjects identified in the UCSD emergency department HIV screening program will be contacted and offered an appointment for study recruitment
3. San Diego Public Health Department (SDPHD) has implemented routine evaluations of their local HIV surveillance data in conjunction with other data to identify PWH who may be OOC³³. This Data to Care program results in the evaluation of ~ 250 new cases per year in San Diego (~20-21 PWH-OOC a month), many of whom are found to be viremic and out-of-care. Once located, SDPHD will offer immediate transportation vouchers (Lyft) to and from the AVRC to expedite study enrollment and rapid ART start.
4. If after 12 weeks enrollment falls below ~7/month we will initiate an additional social media campaign (Facebook and Instagram). We will use the existing UCSD AVRC platform to promote study participation and work within our existing partnerships with local gay bars to increase our social media reach.

Inclusion Criteria:

- 18 years of age or older;
- documented HIV infection status (or rapid HIV will be repeated);
- out-of-care defined as not seen in HIV provider clinic for ≥ 6 months AND not receiving ART for ≥ 1 month (by self-report);
- available for follow-up according to schedule of evaluations.

Exclusion Criteria:

- Co-morbid condition(s) that in the opinion of the investigator could limit the participant's ability to comply with the visit schedule or safely initiate rapid ART (e.g. psychiatric comorbidities or suspected central nervous system opportunistic infection);
- Prior ART regimens that in the opinion of the investigator precludes selection of a treatment option likely to result in virologic suppression (e.g. documented treatment failure on INSTI based regimen and multiple prior NRTI, NNRTI and PI regimens or documented resistance mutations likely to result in treatment failure)
- Participants that are unable to speak sufficient English or Spanish to consent to the study will be excluded

11. RECRUITMENT AND PROCEDURES PREPARATORY TO RESEARCH

Candidates for participation will be recruited through avenues listed in item 10. In situations where clinical data for a subject already exists on UCSD health electronic records, reasonable pre-screening will be undertaken to assess eligibility. A recruitment/educational flyer (Appendix X) is included and will be posted in area clinics, shelters, foodbanks, etc to outreach to potential participants. The text and imagery from the same flyer may also be used as part of a social media outreach effort if we are not reaching our enrollment goals with our initial print media outreach efforts.

For the purposes of pre-screening ONLY: A request for partial waiver of consent is requested.

The investigator believes the pre-screening to be used for recruitment meets the following requirements for this request per 46 CFR 46.116:

1. The (pre-screening) research involves no more than minimal risk to the participants;

2. The waiver or alteration will not adversely affect the rights and welfare of the participants;
3. The (pre-screening) research could not practicably be carried out without the waiver or alteration; and
4. Whenever appropriate, the participants will be provided with additional pertinent information after participation.

Recruitment procedures will also involve the review of participant records by designated study personnel (e.g., investigators and/or study coordinators) in order to identify potentially eligible participants.

Since Protected Health Information (PHI) will be accessed via the study team's record database prior to contacting the potential participant about the research study, we are requesting a partial waiver of HIPAA authorization for access to PHI for purposes of pre-screening only.

Standard HIPAA authorization to collect research data from the participant's medical record will be obtained at the time of informed consent.

A brief subset of preliminary eligibility criteria such as age, diagnosis, co-morbid conditions and prior treatment, will be reviewed by study personnel to determine participants' preliminary eligibility for the research study. No written record of this information will be created. The study coordinator will then approach the participant to further discuss the research study with the participant and ask whether they would like to participate in the study. Eligibility may be formally determined at the time of counseling, but any research-specific screening procedures will only be performed after informed consent is obtained.

For the partial waiver of individual authorization for pre-screening recruitment purposes ONLY of individual HIPAA/Protected Health Information. The following conditions apply:

1. The (pre-screening) research involves no more than minimal risk, since we will not perform any procedure and the probability and magnitude of harm or discomfort anticipated in the research are not greater than those ordinarily encountered in daily life.
2. Granting of waiver for recruitment purposes only will not adversely affect privacy rights and welfare of the individuals whose records will be used. as no written record of the potential participants' information will be created.
3. The pre-screening could not practicably be conducted without a waiver. Obtaining consent from all participants prior to determining eligibility would lead to a high screen fail rate, and as a result, place an increased burden on participants
4. The pre-screening could not practicably be conducted without use of PHI.
5. The privacy risks are reasonable relative to the anticipated benefits of research.
6. An adequate plan to protect identifiers from improper use and disclosure is included in Item 16.
7. Participant identifiers/sensitive information shall be removed/destroyed as soon as they are no longer needed and in accordance with AVRC policy. The investigators have procedures in place to periodically review collected participant identifiers/sensitive information to ensure it is still required to satisfy a particular purpose or carry out a function.
8. The participants' PHI will not be re-used or disclosed for other purposes.

Recruitment to the study will occur through two routes: the first is through identification of UCSD Owen Clinic subjects eligible for recruitment and the second is through referral of participants from the emergency department, SDPHD or through social media campaign to the AVRC. Recruitment to the study will be performed by a named

member of the study team.

UCSD Owen Clinic:

- Participants will be prospectively identified by Owen Clinic and an appointment made at Owen Clinic for re-establishment of care
- At this visit, a study team member will attend UCSD Owen Clinic, assess the subject for eligibility and if eligible perform consent for the study, HIPAA consent and ROI.

AVRC:

- Participants identified through the UCSD emergency department, SDPHD or media campaign will be contacted by the study coordinator and offered an appointment at the AVRC within 7 days. Free Lyft transport will be provided by the study coordinator
- At the AVRC, the project manager will assess the subject for eligibility and if eligible perform consent for the study, HIPAA consent and ROI.

After completion of consent, HIPAA and ROI, the study coordinator will request relevant data from the subject's primary care provider. For subjects under the care of a UCSD provider, one of the study investigators will access the subject's clinical record to abstract relevant information (comorbidities, ART treatment history, HIV resistance assays (genotypes, phenotypes), substance use history, social documentation, baseline laboratory values including HIV VL)

12. INFORMED CONSENT

This protocol, the informed consent document and any subsequent modifications will be reviewed and approved by the UCSD Institutional Review Board responsible for oversight of the study. Written informed consent will be obtained from the participant by a member of the study staff. At the time potential participants contact us regarding the study, any questions they may have will be answered by a member of the study staff. If the potential participant is still interested in participating, the day 0 study visit will continue or be scheduled within 7 days. The participant will be informed of the time that needs to be allotted for their first visit in which the informed consent will be administered.

Individuals unable to speak English will not be excluded from participating in a study. The approved informed consent and any subsequent versions will be translated into Spanish and on a case-by-case situation any other language that is deemed necessary. The translated informed consents will be submitted to the IRB for approval. The consent process will include a qualified translator in the participant's native tongue. If a qualified UCSD translator is not available the Cyrom Language Line will be utilized as they have certified medical interpreters. The interpreter will sign and date at the end of the approved informed consent unless the Cyrom interpreter is utilized. In this situation, the study staff member involved in the consent process will document translator's name, ID#, and date of the translation at the end of the approved informed consent.

The informed consent process will describe the purpose of the study, the procedures to be followed, and the risks, and benefits of participation. This information will be explained to the study participant in a face-to-face setting by the individual consent the participant. Participants will be encouraged to ask questions throughout the consent process and encouraged to discuss their participation with trusted advisors, such as family members, close friends, etc. Participants will be allotted sufficient time to consider whether or not to participate in the research study. After allowing the potential participant time to read the informed consent the study staff and/or investigator will answer and address any questions or concerns the participant may have. Once all questions and concerns have been addressed and the participant wishes to participate, they will be asked to sign the informed consent.

Also, during the consent process, the informed consent process will be documented in the study CRF. A copy of

the consent form will be given to the participant.

